Beijing Science and Technology Program Project Implementation

Topic Title: Research on Early Standardized Electronic
Cognitive Training Technology for Elderly Depression with
Cognitive Impairment

Project Name: Advantageous Discipline Cultivation Project

Field: Healthcare

Category: Public welfare applications

Municipal Science and Technology Commission In charge

of the office: Medical and Health Science and Technology
Division

The version number: 2.0

Document date: September .30.2021

Starting and ending years: January 2020-august 2023

Purpose, significance and necessity of the study

1. Significance and necessity of the study

Age-related depression (LLD) is the most common mental disease in the old age. Because of the increasing prevalence of population aging, it has become one of the important factors affecting the quality of life of the elderly. 50-70% of senile depression is accompanied by cognitive impairment of different degrees. The patients with senile depression with cognitive impairment have higher risk of dementia transformation, worse prognosis and higher recurrence rate, which seriously endanger the quality of life and social function of patients and increase the economic burden of society and families. Therefore, it is urgent to provide evidence-based early intervention strategies for senile depression with cognitive impairment.

At present, the domestic and foreign guidelines do not provide a clear and effective treatment plan for the elderly patients with cognitive impairment, and the clinical research and practice also lack evidence-based treatment. Selective serotonin reuptake inhibitors (SSRIs), the most used antidepressant in elderly depression, cannot significantly improve the cognitive impairment of elderly patients with depression, and may even aggravate the cognitive impairment of elderly patients with depression. The overall efficacy and tolerability of drug therapy for elderly patients with depression and cognitive impairment are poor. Studies have confirmed that cognitive training can significantly improve the overall cognitive function and the functions of multiple cognitive domains of healthy elderly, patients with mild cognitive impairment (MCI) and Alzheimer's disease (AD). The previous research results have also initially confirmed the cognitive improvement effect of cognitive training on elderly patients with depression, providing a new idea for clinical diagnosis and treatment.

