8. Effective rate of treatment: the proportion difference between the two groups of subjects in the reduction rate of hrds-17 scale at each visit point and the baseline $\geq 50\%$.

9. Recurrence rate and recurrence time: recurrence is defined as any of the following conditions: the subject meets the DSM-IV diagnostic criteria for depressive episode; The subject was hospitalized again due to depression; After the treatment was effective (ham-d17 score decreased by $\geq 50\%$ compared with the baseline), ham-d17 score increased by more than 30% compared with the baseline at any visit point; During the maintenance treatment period, after the treatment of the subjects is effective or remission, the proportion of relapse and the time of relapse between the two groups at each visit point;

Safety index:

i. Abnormal values of vital signs, laboratory examination and electrocardiogram examination during the study period.

II. Adverse events and adverse reaction reports during the study period.

Basis for determining sample size

According to the main research hypothesis of this study, the effect of comprehensive intervention group on improving patients' cognition is better than that of conventional treatment group. According to the previous similar research results and the expected efficacy hypothesis, the difference between the groups of the study group and the control group in terms of ADAS cog score reduction after 12 weeks of treatment is about 2.2, and the combined standard deviation is 4. Set $\alpha = 0.025$ (one side), $\beta = 0.20$, and set the superiority and effectiveness limit value as 3 in combination with the

previous research and clinical significance, The ratio of the number of cases in the study group to the control group was 1:1. The sample size of the study group was 51 cases, and the sample size of the control group was 51 cases. Considering the 20% rejection rate of similar items, 64 cases need to be included in the study group and the control group.

Statistical analysis methods

Full Analysis Set (FAS): A collection of all randomized cases with valid baseline assessments. FAS is the main analysis set. Secondary efficacy measures were analyzed using only FAS without carry-over.

General principles: Statistical analysis was performed using SAS.9.4 statistical analysis software. P value < 0.05 was statistically significant (unless otherwise specified).

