Statistical description: Measurement data are described using mean (standard deviation), median (interquartile range), minimum value, and maximum value; skewed distribution indicators are normally corrected before analysis, unless otherwise specified. Enumeration data were described using the number of cases (percentage).

Statistical analysis methods

Full Analysis Set (FAS): A collection of all randomized cases with valid baseline assessments. FAS is the main analysis set. Secondary efficacy measures were analyzed using only FAS without carry-over.

General principles: Statistical analysis was performed using SAS.9.4 statistical analysis software. A P value < 0.05 was statistically significant (unless otherwise specified).

Statistical description: Measurement data are described using mean (standard deviation), median (interquartile range), minimum value, and maximum value; skewed distribution indicators are normally corrected before analysis, unless otherwise specified. Enumeration data were described using the number of cases (percentage).

1) Efficacy analysis:

Primary Endpoint Analysis

The between-group difference in the change from baseline in the total score of the two groups of subjects (ADAS-cog) at the end of 12 weeks

Statistical analysis of changes from baseline in ADAS-cog total scores at the end of 12 weeks was performed using MMRM (mixed model for repeated measures). The model takes the change of ADAS-cog total score at each time point after treatment relative to the baseline as the dependent variable, the baseline ADAS-cog total score is a covariate, and the grouping is a fixed effect. Each fixed effect factor and covariate is nested in each visit. Inside. According to the model, the adjusted mean of the total ADAS-cog total score at the end of treatment in each group compared with the baseline, as well as the difference of the adjusted mean between the two groups and its 95% confidence interval, the lower limit of the confidence interval and the set optimal value were calculated. The comparison of the effect-media value was used as the criterion for superiority.

Secondary endpoint analysis:

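### The superiority limit of 3 ADAS-cog points exceeds the assumed difference of 2.2: 51 per arm fits a test against zero, and if the lower confidence limit must exceed 3, power is about 0.1%, not 80%

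*Combined protocol and SAP*

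**What the plan says.** *Basis for determining sample size* states the hypothesis that the intervention's effect on "cognition is better than that of conventional treatment group". It puts the difference between the groups in "ADAS cog score reduction after 12 weeks of treatment is about 2.2, and the combined standard deviation is 4". With one-sided alpha 0.025, beta 0.20 and 1:1 allocation, it then directs the reader to "set the superiority and effectiveness limit value as 3 in combination with the" earlier research and clinical meaning. The result is given as "The sample size of the study group was 51 cases", with the same number of controls, raised to 64 per arm for a 20% loss. The calculation itself is not shown.

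*Primary Endpoint Analysis* fits a mixed model for repeated measures: "The model takes the change of ADAS-cog total score at each time point after treatment relative to the baseline". From the adjusted group difference and its 95% confidence interval, "the lower limit of the confidence interval and the set optimal value were calculated". It continues: "The comparison of the effect-media value was used as the criterion for superiority". The English is garbled. It gives neither the number nor the sign of the preset value, and the only candidate anywhere in the document is the 3 in the sample-size section.

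**The concern.** In a superiority test with a margin, the assumed true benefit has to lie above the margin. Here it lies 0.8 points below it (2.2 − 3 = −0.8), so the planned effect belongs to the null hypothesis of the test that the limit implies. Adding patients then lowers the power.

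The stated sample size looks as if the limit had not been used at all. If so, the trial was sized for one hypothesis and may be judged on another. The same week-12 result, for example an estimated benefit of 2.5 points with a confidence interval above zero, would be a success under one reading and a failure under the other. That choice concerns the primary endpoint and should not be open once data have been seen.

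**Working it through.** **Inputs** (all from *Basis for determining sample size*): difference 2.2; SD 4; one-sided alpha 0.025 (z = 1.960); power 80% (z = 0.842); limit M = 3; 51 per arm evaluable; 64 per arm enrolled. The lower limit of the two-sided 95% interval in *Primary Endpoint Analysis* corresponds to one-sided 0.025.

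**1. Reproducing the stated size.** n per arm = 2 × (1.960 + 0.842)² × 4² / (2.2 − M)².

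- M = 0: 51.9, which rounds up to 52 (53 with the t distribution). The plan states 51, so the match is within one or two patients.
- Loss: 51 / (1 − 0.20) = 63.75, giving the stated 64.
- M = 3: the formula returns 392, but only because −0.8 is squared. The gap has the wrong direction, so this is not a valid size, and it is not 51.
- M = −3 (gap 5.2): 9.3.
- An effect of 3 tested against zero: 27.9.

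With 2.2 taken as the group difference, no use of 3 gives 51.

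**2. Standard error.** SE = 4 × √(2/n) = 0.792 at n = 51 and 0.707 at n = 64.

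**3. Power at a true difference of 2.2 under each reading.**

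| Rule | Formula | 51 per arm | 64 per arm |
|---|---|---|---|
| (a) Lower limit of benefit above 3 | Φ((2.2 − 3)/SE − 1.96) | 0.15% | 0.10% |
| (b) Lower limit of benefit above 0 | Φ(2.2/SE − 1.96) | 79.3% | 87.5% |
| (c) Signed change, lower limit above −3 | Φ((3 − 2.2)/SE − 1.96) | 17% | 20% |

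The t-based values are 0.15% and 0.10% for (a), and 78.5% and 87.0% for (b).

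**4. What (a) would require.**

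- Observed difference: 3 + 1.96 × SE = 4.55 (n = 51) or 4.39 (n = 64).
- True difference for 80% power: 3 + 2.80 × SE = 5.22 or 4.98.
- At 100 per arm, power falls to 0.037%.
- If the SD is assumed to be anywhere from 3 to 5, power at 51 per arm stays between 0.05% and 0.28%.

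**5. Why the sign matters.** The model's outcome is change from baseline, so improvement is negative and the planned intervention-minus-control difference is −2.2. If an analyst kept the lower limit and compared it with −3, the rule would be met with probability Φ(3/SE − 1.96) = 97% (n = 51) or 99% (n = 64) when training has no effect. Reading (c) is hypothetical, because −3 does not appear in the document. It shows what an unstated sign allows, and it is not a test of benefit.

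**The case against.** The strongest reply is that the 0.1% depends on one reading of a badly translated paragraph that contains neither the number 3 nor a sign. If the test is against zero, the trial has close to its planned power. That is true, and the power figure is conditional for this reason. What does not depend on the translation is that 2.2, 3 and 51 are legible in one paragraph and do not fit together.

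A second point has weight. The sample-size formula depends only on the difference minus the margin, so 51 per arm cannot by itself separate a 2.2-point effect tested against zero from a 5.2-point effect tested against 3 (power 79.3% at 51 in both). Only the wording decides, and the text gives 2.2 as the difference between the groups, not as the excess over 3. The match to zero is therefore an inference for the sponsor to confirm.

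Third, *General principles* calls P < 0.05 significant. That line applies unless otherwise specified, and the primary analysis specifies its own superiority criterion. It does not settle the matter.

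Fourth, moving to a test against zero selects the easier hypothesis, although the plan ties its limit to clinical meaning. This is a real cost, and it is why the derivation must be shown first and the change disclosed.

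Finally, the figures at 64 per arm assume no missing week-12 data, and all figures use the unadjusted SD. Adjustment for baseline would shrink the SE. That raises power under (b) and lowers it further under (a).

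**Conclusion.** The point holds. The stated limit of 3 and the stated 80% power at a difference of 2.2 cannot both stand. If the lower limit of the benefit must exceed 3, power is 0.15% at 51 per arm and 0.10% at 64, and no sample size reaches 80%. Against zero, power is 79% at 51 per arm and 88% at 64. No sign convention for a limit of 3 gives a superiority test with 80% power at the stated assumptions.

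The inconsistency between 2.2 and 3 is certain. The power of about 0.1% assumes that the preset value in the primary analysis is the 3 from the sample-size section, applied to benefit counted as positive, with an SD of 4. This must be fixed, because it determines what counts as success on the primary endpoint.

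**What to change.** 1. Show how 51 per arm was calculated, and state whether 2.2 is the group difference or the excess over 3.
2. Reconcile the assumed effect, margin, sign and decision rule across *Basis for determining sample size* and *Primary Endpoint Analysis*, in a documented and disclosed amendment made before any unblinded data are seen.
3. Unless 2.2 proves to be misreported, test superiority over zero, which is what the stated hypothesis implies. Suggested text: *The difference is the score reduction in the training group minus the score reduction in the control group; positive values favour training. Success is a two-sided 95% confidence interval for the week-12 difference that lies wholly above 0.* Report 3 points only as a clinical-relevance benchmark beside the estimate and its interval.
4. If 3 is kept as the margin, withdraw the 80% claim and state the actual power: about 0.1% at a true difference of 2.2, and 80% only at about 5.

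**Cost.** Two paragraphs change, and a test against zero needs no added patients or visits. It is still more than wording: it settles the primary hypothesis, makes success easier than under a margin of 3, and gives up any claim that a positive result shows a benefit above 3 points. The document is dated September 2021 and its front page reads "Starting and ending years: January 2020-august 2023", so the change may fall mid-trial. Its date and the blinding status at that time must be reported.

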5) Activities of daily living (ADL): the cognitive function of the subjects was assessed in the baseline period, 2 weekends, 4 weekends, 8 weekends, 12 weekends, 26 weekends, 38 weekends and 52 weekends.

Safety evaluation

1) Vital signs: the temperature, pulse and blood pressure of the subjects were monitored at the end of the baseline period, 2 weekends, 4 weekends, 8 weekends, 12 weekends, 26 weekends, 38 weekends and 52 weekends.

2) Adverse event report: adverse event records were made on the subjects at the end of the baseline period, the end of the 2nd week, the end of the 4th week, the end of the 8th week, the end of the 12th week, the end of the 26th week, the end of the 38th week and the end of the 52nd week.

3) Treatment Emergent Symptom Scale (TESS): during the baseline period, the subjects were evaluated for side effects at the end of 2 weeks, 4 weeks, 8 weeks, 12 weeks, 26 weeks, 38 weeks, and 52 weeks.

4) Laboratory examination and electrocardiogram: routine blood test, biochemical examination and electrocardiogram examination were conducted at the end of the

screening period, the end of the 4th week, the end of the 12th week, the end of the 38th week and the end of the 52nd week.

Efficacy index

1) Main efficacy indicators:

At the end of the 12th week after treatment, the change value of ADAS cog scale scores of the subjects in the two groups compared with the baseline.

2) Secondary efficacy indicators:

1. At each follow-up point, the change value of ADAS cog scale scores of the two groups compared with the baseline.

2. At each follow-up point, the change value of hrsd-17 score of the subjects in the two groups compared with the baseline;

3. At each follow-up point, the change value of HAMA scale scores of the two groups compared with the baseline.

4. At each follow-up point, the change value of GDS score of the subjects in the two groups compared with the baseline.

5. At each follow-up point, the change value of NPI scale scores of the subjects in the two groups compared with the baseline.

6. At each follow-up point, the change value of ADL scale scores of the subjects in the two groups compared with the baseline.

7. Complete remission rate: the difference in the proportion of patients with a total score of hrds-17 ≤ 7 at each visit point between the two groups.

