Efficacy evaluation indicators include HRSD-17, HAMA, GDS, NPI, ADL and other scales. The differences between groups at the visit point relative to the baseline value were analyzed using the same analysis method as the main efficacy indicators. The cumulative complete remission rate, treatment response rate, recurrence rate and other outcome indicators during the study period were compared between groups using the Kaplan-Meier curve, and the COX proportional hazards model was used to evaluate the impact of the intervention while controlling for confounding factors such as disease duration.

Safety analysis: The incidence of adverse events and adverse reactions was tested by chi-square and described in a list.

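### The blanket P < 0.05 rule lets any of 35 to 41 secondary scale-by-visit contrasts be called statistically significant, with no hierarchy, adjustment or exploratory label

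*Combined protocol and SAP*

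**What the plan says.** The section Statistical analysis methods appears twice in the combined document: once after the sample size paragraph, and again ahead of the efficacy analysis. Both copies carry the same general principle. The second reads "A P value < 0.05 was statistically significant (unless otherwise specified").

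Under Efficacy index, the primary is a single contrast, ADAS-cog change from baseline at week 12. The secondary list then opens with "At each follow-up point, the change value of ADAS cog scale scores of the two groups compared with the baseline" and repeats that form for HRSD-17, HAMA, GDS, NPI and ADL. Remission, response and recurrence follow.

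Under Secondary endpoint analysis, the scales are handled inferentially: "The differences between groups at the visit point relative to the baseline value were analyzed using the same analysis method as the main efficacy indicators". Remission, response and recurrence are compared by Kaplan-Meier curves and a Cox model.

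Only the primary has a criterion of its own. The sample size section sets a one-sided alpha of 0.025, and the primary analysis compares a limit of the 95% confidence interval with a preset superiority value.

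**The concern.** A blanket threshold does no harm if the plan also says which results it may be used to claim. This plan does not. A reader who applies it literally may attach the label of statistical significance to any secondary scale at any visit. Nothing ranks those results, adjusts for their number, or marks them as exploratory.

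Five of the six scales measure mood, anxiety, neuropsychiatric symptoms or daily function, while the main research hypothesis concerns cognition. If the week-12 ADAS-cog comparison failed, a report could still describe a significant benefit on one of those scales at one of seven visits without breaking any written rule. The project means to supply evidence for treatment guidelines, so such a statement would carry weight. The 0.025 used to size the trial covers one test. It does not cover the set of significance statements that the plan permits.

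**Working it through.** **The plan's own figure.** The documents give no count of tests and no family-wise error rate. Their only error-rate calculation is the sample size for the primary. Inputs from the sample size section: difference "in terms of ADAS cog score reduction after 12 weeks of treatment is about 2.2"; "the combined standard deviation is 4"; one-sided alpha 0.025; beta 0.20; allocation 1:1.

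- n per arm = 2 × [4 × (1.960 + 0.842) / 2.2]² = 51.9, so 52 after rounding up. The plan states 51, at which power is 79.3%.
- 51 / (1 − 0.20) = 63.75, so 64 per arm, as stated.

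This reproduces the plan to within one patient per arm, provided the superiority limit of 3 is left out. That limit is a separate question. The point here is that the calculation covers one contrast only.

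**Counting the contrasts.**

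- Visits after baseline: weeks 2, 4, 8, 12, 26, 38 and 52, which is 7 (Symptomatic assessment).
- Scales: ADAS-cog, HRSD-17, HAMA, GDS, NPI and ADL, which is 6 (Secondary efficacy indicators).
- All scales at all visits, less the primary: 6 × 7 − 1 = 41.
- Symptomatic assessment lists the visits for five scales but not for ADAS-cog. Its seven visits are inferred from the overall design, which has cognitive scales done at each visit, and from the wording of the first secondary indicator. If ADAS-cog were measured only at week 12, 5 × 7 = 35 contrasts remain.
- Adding remission and response at each of seven visits would give 41 + 14 = 55, before recurrence. These are left out below.

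**Expected false positives if training has no effect.** The general principle does not state sidedness; 0.05 is taken as two-sided.

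| Contrasts | Either direction (× 0.05) | Favouring training (× 0.025) |
|---|---|---|
| 35 | 1.75 | 0.875 |
| 41 | 2.05 | 1.025 |

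These averages do not depend on how the tests are correlated.

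**Chance of at least one false positive, 41 contrasts.** If independent: 1 − 0.95⁴¹ = 87.8% in either direction, and 1 − 0.975⁴¹ = 64.6% favouring training. The contrasts share patients and constructs, so they are not independent. The documents give no correlations. The values below are assumptions, with one common correlation between scales and one between visits, evaluated by simulating correlated normal test statistics.

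| Correlation, scales / visits | Either direction | Favouring training |
|---|---|---|
| Independent | 88% | 65% |
| 0.3 / 0.6 | 70% | 39% |
| 0.5 / 0.7 | 58% | 30% |
| 0.6 / 0.8 | 46% | 23% |

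The right-hand column matches the harm at issue, a false claim of benefit. For comparison, the sample size section allows 2.5% for that error on the primary.

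**The case against.** The strongest reply is that the trial's confirmatory inference is already sound in this respect. There is one primary endpoint at one time point, the main hypothesis is tied to it, and everything else is labelled secondary. Secondary results are commonly read as supportive, and P < 0.05 is a generic convention. This stands as far as the primary goes. It does not dispose of the point, because the plan never says that secondary results are supportive only, and its general rule gives them the significance label.

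A second reply is that the secondary scales use the same method as the primary, which might bring the confidence-limit criterion with it. The text is unclear on this. The only limit given is "set the superiority and effectiveness limit value as 3", in the ADAS-cog sample size paragraph, so this reading could touch at most the six other ADAS-cog contrasts. The remaining 35 would still fall under the P < 0.05 rule.

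Four stronger readings are tempting and should not be drawn:

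- That the primary's type I error is inflated. It is a single prespecified contrast, and the secondary tests do not alter it.
- That about two false claims of benefit are expected. That figure counts both directions; about one would favour training.
- That the plan declares every secondary contrast significant. It sets a threshold and declares nothing.
- That the plan says a secondary result may stand in for a failed primary. It does not say so. The gap is that nothing rules such a claim out.

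**Conclusion.** The point holds for significance claims on secondary efficacy endpoints. The written rule allows 35 to 41 scale-by-visit contrasts to be called statistically significant without control of the error rate across them. Under no effect, 1.75 to 2.05 false positives are expected, about 0.9 to 1.0 of them favouring training. The chance of at least one false result in training's favour, with 41 contrasts, runs from 23% to 65% over the correlations considered.

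This rests on three assumptions: a two-sided 0.05, no true effect on any scale at any visit, and correlations that are illustrative. The upper count also relies on the inferred ADAS-cog schedule. Leaving out remission, response and recurrence makes the count conservative. Since the primary test is untouched, this is an inexpensive improvement to what the trial may claim and does not put its main result in doubt.

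**What to change.** Amend the general principle in both copies of Statistical analysis methods, so that no contradictory copy remains. Suggested wording:

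> For efficacy, statistical significance is claimed only for the primary endpoint, ADAS-cog change from baseline at week 12, judged by its own prespecified criterion (one-sided 0.025, applied through the 95% confidence interval). All secondary efficacy results are reported as estimates with 95% confidence intervals; their P values are nominal and support no claim of significance. Safety comparisons are descriptive.

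The primary criterion has to be named, because otherwise the amendment removes the only general threshold without saying what governs the primary. The safety sentence is needed because chi-square tests are planned for adverse events.

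The cost is a few sentences, with no change to patients, data, model or sample size. The downside is that no secondary endpoint can be reported as significant. If the sponsor wants such a claim for one or two endpoints, a short ordered list of key secondary contrasts, each at a named visit and tested only after success on the primary, would be the alternative.

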no more than 2 times in each training cycle; In addition to the above fixed training, if the training content does not reach 16 items / week, cognitive training in other fields will be randomly pushed; Within each training day, only one cognitive rehabilitation training is arranged for each cognitive field; The difficulty of each cognitive rehabilitation training depends on the last training level of the subject.

Training scheme of the control group: to keep the same electronic use time as that of the intervention group, the subjects in the control group are required to open the electronic products for 60 minutes every day, 4 days a week.

Intervention mode

Tablet computer or mobile phone to be used in this intervention training. The training will take the principles of psychology and cognitive neuroscience as the core, and interactive games as the carrier, covering the cognitive training in six fields: episodic memory, executive function, working memory, processing speed, speech ability and reasoning judgment, to ensure the scientific on the premise of enhancing interest.

According to their own conditions, the subjects can choose to go to the hospital to use the tablet computer provided by the hospital for training within the reserved time or can use their own tablet computer or mobile phone for independent training. The training mode of this intervention is flexible. The subjects can start training on different terminal devices, and the training records can also be updated in real time. The research team will monitor the whole training process.

Research object

Inclusion criteria: 1. written informed consent signed by patients and their families; 2. Age ≥ 60 years; 3. Meet the diagnostic criteria for single or recurrent major depressive disorder in the diagnostic and Statistical Manual of mental disorders Fourth Edition (DSM-V); 4. Currently in the acute phase, the total score of hrds-17 at baseline is ≥ 18 points. 5. There were cognitive impairment symptoms, and the Montreal Cognitive Assessment Scale (MoCA) was < 26 points. 6/ Education level above primary school.

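### The primary MMRM adjusts only for baseline ADAS-cog; prespecifying baseline HRSD-17, which every patient has, would probably buy some precision at almost no cost

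*Combined protocol and SAP*

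**What the plan says.** **Primary endpoint.** Efficacy index defines it as "At the end of the 12th week after treatment, the change value of ADAS cog scale scores of the subjects in the two groups" relative to baseline.

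**Primary model.** Statistical analysis methods, Primary Endpoint Analysis, specifies an MMRM in which "the baseline ADAS-cog total score is a covariate, and the grouping is a fixed effect". It adds that "Each fixed effect factor and covariate is nested in each visit", so arm and baseline ADAS-cog each have visit-specific effects. Nothing else is listed.

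**Baseline data.** The inclusion criteria (Research object) set a minimum of 18 points for "the total score of hrds-17 at baseline is", and Symptomatic assessment schedules HRSD-17 at baseline. Every eligible patient therefore has a value. The criteria also require age of at least 60 and "Education level above primary school". The documents do not say in what form age and education are stored.

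**Allocation.** Overall design scheme describes random allocation to two arms and names no stratification factor.

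**Other adjustment.** Secondary endpoint analysis evaluates the intervention in Cox models "while controlling for confounding factors such as disease duration". The primary analysis has no counterpart to this.

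**The concern.** Patients enter in an acute depressive episode and receive an SSRI. The protocol's review of research at home and abroad describes cognitive impairment that may lift as depression lifts but persists in some patients. On that account, entry depression severity could explain part of the variation in 12-week cognitive change that baseline ADAS-cog does not. A prognostic variable measured on everyone but left out of the model leaves its variance in the error term, and the confidence interval for the treatment difference is wider than it need be.

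This matters more because power has no slack. The stated 51 evaluable patients per arm sits slightly below what the plan's own inputs require, so even a modest gain would bring t-test power back above 80%.

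**Working it through.** **Inputs from Basis for determining sample size.** The expected difference "in terms of ADAS cog score reduction after 12 weeks of treatment is about 2.2"; "the combined standard deviation is 4"; one-sided alpha 0.025; power 80%; 1:1 allocation; 51 evaluable and 64 enrolled per arm with 20% loss.

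**Inputs assumed.** R² is the share of residual variance, beyond baseline ADAS-cog, that the added covariates explain. The documents give no value; I use 0 to 15%. I treat the SD of 4 as the residual SD of the present model and approximate the week-12 MMRM contrast by a two-sample comparison with 51 per arm.

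**Step 1: reproduce the plan's sample size.** n = 2 × (1.960 + 0.842)² × 4² / 2.2² = 51.9, so 52 per arm against 51 stated. Allowing for loss, 51 / 0.80 = 63.75, so 64 per arm, as stated. The figure reproduces as a test against zero difference, without the margin of 3 and without credit for extra covariates.

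**Step 2: precision and power of the present model.** SE = 4 × √(2/51) = 0.792. The noncentrality is 2.2 / 0.792 = 2.78. With 100 degrees of freedom the t-test power is 78.5%.

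**Step 3: add covariates.** SE = 0.792 × √(1 − R²). Power is from the noncentral t, with three further degrees of freedom spent. The 95% half-width is 1.96 × SE.

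| Assumed R² | SE | 95% half-width | Power for 2.2 against zero |
|---|---|---|---|
| 0 | 0.79 | 1.55 | 78.5% |
| 2% | 0.78 | 1.54 | 79.3% |
| 5% | 0.77 | 1.51 | 80.5% |
| 10% | 0.75 | 1.47 | 82.6% |
| 15% | 0.73 | 1.43 | 84.7% |

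The three degrees of freedom cost almost nothing: at R² = 0, power moves from 78.54% to 78.52%.

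**Step 4: where chance imbalance sits.** The part of the unadjusted estimate due to chance imbalance in the covariates has mean zero over randomisations and SD 4 × √R² × √(2/51). At R² = 10% this is 0.25 points. The variances add: 0.751² + 0.250² = 0.564 + 0.063 = 0.627 = 0.792². Imbalance is therefore already inside the SE of 0.79.

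**The case against.** **The model already contains the best predictor.** The baseline of the outcome, fitted by visit, usually explains most of what can be explained. Age and education may act mainly on the level of ADAS-cog, which that covariate absorbs, and eligibility narrows the range of every candidate. This stands: at R² of 2% or less the gain is under one point of power.

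**A reader might infer that the primary estimate is biased, or that nothing balances these factors.** The documents do not support that. Randomisation balances them in expectation and keeps the estimate unbiased and the interval valid. No stratification factor is named, so none has been left out of the model.

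**A reader might count chance imbalance as a second harm.** For example, a 0.3 SD imbalance in a covariate with an assumed partial correlation of 0.3 shifts the estimate by 0.3 × 0.3 × 4 = 0.36 points, or 16% of 2.2. That is 0.36 / 0.79 = 0.45 of one SE, in either direction. Step 4 shows that such shifts are the lost precision seen in a single trial.

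**A reader might take age and education as recorded for analysis.** Only entry thresholds are given. Baseline HRSD-17 alone is explicitly scheduled.

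**The Cox comparison is weak support.** It names only disease duration, as an example, and does not point to HRSD-17, age or education. It shows that adjustment was considered for secondary outcomes, but does not settle which set to use.

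**The power figures test against zero.** Primary Endpoint Analysis appears to compare the lower confidence limit with the superiority value, which the sample size section sets at 3. On that reading, power at a true difference of 2.2 is about 0.1% with or without added covariates. This is correct, and it is a separate and larger problem.

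**Conclusion.** The point holds as an efficiency improvement. The primary MMRM leaves out a baseline measurement that the trial takes on every patient and that plausibly predicts the outcome, so precision is probably lost. For 2.2 points against zero with 51 per arm, the gain in power runs from about 1 point (R² 2%) through 2 and 4 points to about 6 points (R² 15%), and the SE falls from 0.79 to between 0.78 and 0.73.

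The size rests on an R² that the documents do not supply, on reading the SD of 4 as the residual SD, and on the two-sample approximation. What does not depend on R² is that the model names only arm and baseline ADAS-cog, that baseline HRSD-17 is available, and that three extra degrees of freedom cost little at this sample size. The present analysis is not in error, and the case is firmer for HRSD-17 than for age or education.

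**What to change.** Before any unblinded data are seen:

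- Add baseline HRSD-17, as a continuous variable, to the prespecified covariates of the primary MMRM beside baseline ADAS-cog.
- Confirm whether age and education are recorded as analysable values. If so, add them in a defined form (age continuous; education as years or as listed categories). If not, leave them out.
- State whether the added covariates are crossed with visit, as the present covariate is, or enter as single terms.
- Use the same set in the secondary MMRMs, and report the present model as a sensitivity analysis.

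**Cost.** A sentence or two in the analysis section and no new assessments. As single terms, three covariates use about three degrees of freedom, more if education is categorical. Crossed with visit they use more: if ADAS-cog follows the seven post-baseline visits listed for the other scales, 3 × 7 = 21 coefficients, or 7 for HRSD-17 alone. If the covariates prove weak, there is little or no gain. The margin of 3 has to be resolved separately.
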